Efficacy Evaluations	
Expected Results and interpretation:
 
Our aim is to develop a panel of biomarkers and an algorithm for calculating a Cho status score that correlates well with measures of Cho pool size by isotope dilution. We will define the minimum set of biomarkers that provides >90% accuracy in predicting Cho pool size measured by isotopic dilution. We expect to see incremental declines in Cho status, as reflected in the panel of biomarkers. Results on the 100% diet should be similar to what we previously published. In the earlier studies, subjects were fed the 10% diet for a period of 2 to 7 weeks; in the proposed study, we feed 25%, 50%, and 100% (adequate intake) diets for two weeks (order randomly assigned) with 2 week washout periods in between. We expect that our results on the 25% & 50% diets will be less than those previously described; i.e. there will be smaller difference in the biomarkers than previously described. We expect that the 25% & 50% diets will show changes in Cho pool size and in biomarkers that fall between 100% and 10% values. Genotype will change the rate at which a diet treatment alters Cho pool size but will not affect whether our biomarker panel correlates with the pool size achieved. Thus, we do not have to power the study for genotype differences.

Pharmacokinetic Evaluations	N/A
Safety Evaluations	After each diet period a clinical chemistry panel will be run to assess potential liver and muscle damage. If any damage is noted after any of the dietary periods (liver damage = >1.5-fold increase in aspartate aminotransferase (AST) alanine transaminase (ALT) or muscle damage = >5-fold increase in creatine phosphokinase (CK)), affected subjects will follow the abnormal lab value protocol chart (See Appendix Figure 6). This will be reported to the IRB and the subject will be monitored and re-tested according to protocol and until AST/ALT and CK values return to normal.

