depletion was associated with abnormal renal function in animal models (62); a number of metabolites that accumulate in people with diminished renal function, including 3-carboxy-4-methyl-5-propyl-2-furanpropanoate (CMPF), hippurate and 3-indolepropionate also were significantly increased by Cho depletion in our study subjects (10). Cho is important for mitochondrial function (63, 64), and in our study, plasma concentrations of several acylcarnitines were increased, reflecting perturbed mitochondrial function (65). In addition, people with SNPs that increase susceptibility to Cho deficiency had > 50% increased concentrations of propionylcarnitine (10). Plasma concentrations of a number of amino acids and their metabolites increased in Cho depletion (glutamine, pyroglutamate, glycine, valine, glutamyl-valine, and leucine) (10). Finally, plasma concentrations of a number of metabolites released from dying cells (urate and pseudouridine) were elevated in Cho depleted subjects (10). The alterations associated with Cho depletion in most metabolites were at least partially corrected by Cho repletion (10).

When people were depleted of Cho they developed abnormal aspartate transaminase (AST; marker of liver damage) and creatine phosphokinase (CK; marker of muscle damage) activities in blood (24, 52). This occurs because Cho deficiency induces apoptosis in tissues (26, 66, 67). Development of fatty liver was also a marker for Cho depletion in people fed low Cho diets (24, 25, 52, 55). Previously, we used mass resonance imaging to quantitate the fatty liver that occurred with Cho depletion (24) but this method is expensive and we believe that other non-invasive methods can be used to assess fatty liver. Controlled Attenuation Parameter (CAP) is a new ultrasound-based technique to measure steatosis simultaneously with assessment of liver stiffness using transient elastography (TE); it has been used in research studies (68-72) and is being used in hepatology clinics (73, 74). The measures of organ dysfunction discussed above, could improve a panel of other biomarkers by providing information assessing likely organ effects associated with Cho depletion. Though we expect elevations in these markers, we do not anticipate clinically significant damage based on this study design (see Safety).

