There may be subjects that do not have the freezer capacity to store food and will have to make more frequent visits to pick up food.

4.5 Concomitant Medication documentation:

All concomitant prescription medications taken during study participation will be recorded on the case report forms (CRFs). For this protocol, a prescription medication is defined as a medication that can be prescribed only by a properly authorized/licensed clinician. Medications to be reported in the CRF are concomitant prescription medications, over-the-counter medications and non-prescription medications.

4.6 Rescue medication administration: N/A.

Subject Completion/Withdrawal procedures: Subjects can withdraw from the study at any time without penalty. The investigators have the right to stop their participation any time due to any clinical adverse event (AE), laboratory abnormality, or other medical condition or situation occurs such that continued participation in the study would not be in the best interest of the participant, failure to follow instructions (noncompliance with administered diet), or because the entire study has been stopped. Participants who withdraw or are terminated from the study will have normal Comprehensive metabolic panel results at the time of discharge. If they do not, they will follow the established abnormal lab values protocol (See Appendix Figure 6), and the Comprehensive metabolic panel will be repeated weekly until all values are within normal range. Subjects will be compensated for the days spent in the study.

4.7 Screen Failure procedures:

Subjects failing the screening visit (Visit 1) will receive \$25 cash and will be informed that they are not eligible.

5 STUDY EVALUATIONS AND MEASUREMENTS (how measurements will be made)

5.1 Efficacy Evaluation (if applicable):

Biomarker panel:

Based on the discussion above, we selected the following biomarker panel for evaluation: Direct measures of Cho-derived pools: Cho, betaine, dimethylglycine, homocysteine, methionine, PtdCho, sphingomyelin, sarcosine, trimethylamine and trimethylamine oxide.

Measures of Cho-sensitive renal function: Plasma 3-carboxy-4-methyl-5-propyl-2-furanpropanoate (CMPF), hippurate and 3-indolepropionate.

Measures of Cho-sensitive mitochondrial function: Plasma acylcarnitines.

Measures of Cho-sensitive amino acid metabolism: Plasma glutamine, glutamyl-valine, glycine, leucine, pyroglutamate and valine.

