Measures of Cho-sensitive liver & muscle damage: Plasma AST and CK; Controlled Attenuation Parameter (CAP).

This panel of biomarkers will be measured by targeted metabolomic profiling using LC-MS and GC-MS platforms, by targeted standard clinical assays of AST and CK activities in plasma, and by vibration-controlled transient elastography (Controlled Attenuation Parameter) assessment of fatty liver using a Fibroscan® M Probe.

Targeted metabolomic profiling of Cho-related metabolites: Plasma Cho, betaine, sphingomyelin and PtdCho (76, 77), dimethylglycine (78) and homocysteine (79) will be measured using liquid chromatography multiple reaction monitoring mass spectrometry coupled to stable isotope dilution. These methods are running in our laboratory and we have published extensively using the methods (e.g. (52, 55, 77, 80-83)). We use some deuterated internal standards in this assay, and plan to use ¹³C and ¹⁵N internal standards to replace these because of the use of deuterium in the isotope dilution studies. We will perform appropriate QC analysis to assure these substitutions do not alter the accuracy of our assays. Our method easily distinguishes deuterated Cho-containing compounds from C₁₂ forms.

Acylcarnitines: Plasma acylcarnitines will be measured using liquid chromatography multiple reaction monitoring mass spectrometry coupled to stable isotope dilution (84, 85). Acylcarnitines are byproducts of lipid oxidation and even-chain species arise from incomplete β-oxidation of fatty acids, whereas odd-chain species such as C3 and C5 are produced during amino acid catabolism (86-88).

Clinical chemistry panel (comprehensive metabolomic panel {CMP}): At beginning and the end of each diet period (6 times total) all subjects will have urine and a blood sample obtained. Blood or urine will be tested for a Comprehensive Metabolic Chemistry Panel (Chem12) that includes: glucose, calcium, albumin, total protein, sodium, potassium, CO₂, Chloride, BUN, creatinine, CK, ALP, ALT, AST, and bilirubin. This test will be performed Carolinas Medical Center (CMC), which is both Clinical Laboratory Improvement Act and College of American Pathologists accredited. Creatine kinase (CK) will also be obtained.

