6.2 Secondary Endpoint

SubAim 1c: Determine whether people with genetic polymorphisms known to increase risk for developing choline deficiency-induced organ dysfunction are also more likely to have a worse choline status score and a reduction in choline pool size assessed using isotope dilution. A number of SNPs in genes of choline and folate metabolism have been associated with increased risk for developing organ dysfunction on a low choline diet. We hypothesize that people with these SNPs have a lower choline pool size/worse choline status score for any given choline dietary intake than do people without these SNPs.

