15 APPENDIX

Figure 1

Repeat the above for 50% Cho (275 mg/d) and 100% Cho (550 mg/d). Arms performed in random order with minimum 2 week washout in between.

Figure 1 outlines what each 2 week intervention period is comprised of. This will be completed 3 times per subject.

[figure not shown]
Figure 2

Figure 3

Pathway	Metabolite	Platform ²	Fatty liver		Muscle dysfunction		No dysfunction	
			D/B ¹	R/D ¹	D/B ¹	R/D ¹	D/B ¹	R/D ¹
Choline metabolism	Choline	T-LC/MS	0.67	1.50	0.66	1.25	0.71	NA
	Sarcosine	T-GC/MS	0.47	2.00	0.60	1.08	0.56	NA
	Dimethylglycine	T-GC/MS	0.51	1.81	0.55	1.41	0.59	NA
	Betaine	T-LC/MS	0.45	1.66	0.53	1.07	0.47	NA
	Methionine	T-GC/MS	0.86	1.10	0.93	1.01	0.96	NA
	Phosphatidylcholine (total)	T-LC/MS	0.89	1.08	0.90	1.06	0.97	NA
Carnitine metabolism	Homocysteine	T-GC/MS	1.16	0.97	1.19	0.99	1.27	NA
	Carnitine	N-LC/MS+	1.41	0.84	1.23	1.02	1.42	NA
	Butyrylcarnitine	N-LC/MS+	1.23	0.89	1.03	1.13	1.30	NA
	Isobutyrylcarnitine	N-LC/MS+	1.09	1.12	0.88	1.44	1.41	NA
	Isovalerylcarnitine	N-LC/MS+	0.75	1.36	1.01	0.88	0.87	NA
Renal transporter	Propionylcarnitine	N-LC/MS+	1.02	0.99	1.38	1.38	1.78	NA
	Hippurate	N-LC/MS+	0.53	1.88	0.93	0.72	0.75	NA
	3-indolepropionate	N-LC/MS+	0.74	1.03	1.08	0.62	0.50	NA
	CMPF	N-LC/MS-	0.46	0.86	0.57	0.74	0.32	NA
Keto acid metabolism	Creatinine	N-LC/MS+	1.00	0.95	1.00	1.00	1.12	NA
	Myo-inositol	N-GC/MS	0.70	1.22	0.85	1.13	0.76	NA
	Pyridoxate	N-LC/MS-	0.71	1.18	0.93	1.09	0.82	NA
Cell death	Erythronate	N-GC/MS	1.11	0.90	1.21	0.97	1.24	NA
	Urate	T-Clin Lab	1.19	0.90	1.39	0.92	1.22	NA
Amino acid metabolism	Pseudouridine	N-GC/MS	1.17	0.92	1.28	0.98	1.20	NA
	Glutamine	N-LC/MS+	1.07	0.87	1.06	0.98	1.12	NA
	Pyroglutamate	N-LC/MS-	1.29	1.06	1.08	1.03	1.36	NA
	Valine	N-LC/MS+	1.03	1.01	0.97	1.06	1.13	NA
	Glutamylvaline	N-LC/MS+	1.19	0.91	1.37	1.20	1.47	NA
	Glycine	N-GC/MS	1.12	0.89	1.09	0.98	1.09	NA
	Leucine	N-LC/MS+	1.01	1.03	0.87	1.45	1.25	NA
	Trans-4-hydroxyproline	N-GC/MS	1.01	1.35	0.70	0.89	1.18	NA
Diet	Stachydrine	N-LC/MS+	0.06	5.39	0.10	0.86	0.03	NA
Fatty liver	Ratio of liver fat to spleen fat	MRS	1.55	0.72	1.18	0.82	1.12	NA
	X - 02249	N-LC/MS-	0.63	1.60	0.57	0.98	0.67	NA
Unknown	X - 09789	N-LC/MS-	0.30	2.98	0.23	1.71	0.32	NA
	X - 11315	N-LC/MS+	0.82	0.95	1.03	0.92	0.84	NA

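### No planned model tests whether the score-to-pool relation is the same across genotypes, so SubAim 1c could read a direct genotype shift in the score as validation

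*Combined protocol and SAP*

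**What the plan says.** The Synopsis (Efficacy Evaluations) says that genotype changes how fast a diet alters pool size but "will not affect whether our biomarker panel correlates with the pool size achieved". It concludes: "Thus, we do not have to power the study for genotype differences". Read literally, the claim is about correlation.

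Section 1.1 reports from the group's earlier depletion study that "people with SNPs that increase susceptibility to Cho deficiency had > 50% increased concentrations of propionylcarnitine". It does not give the comparator, the diet phase, the pool size or the SNPs. Section 5.1 lists in the panel "Measures of Cho-sensitive mitochondrial function: Plasma acylcarnitines". The class is named but the individual species are not, although the assay description notes that "odd-chain species such as C3 and C5 are produced during amino acid catabolism", and C3 is propionylcarnitine.

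SubAim 1c is hypothesis-driven (Section 6.2): "We hypothesize that people with these SNPs have a lower choline pool size/worse choline status score for any given choline dietary intake". The genotyping part of Section 5.1 presents this as a check on the validity of both the score and the isotope dilution measure, and allows that carriers' biomarkers may be altered. Section 6.3 fits the score on diet, genotype and diet-by-genotype with a random subject effect, then applies the same model to pool size. It sets aside confounding by genotype because each subject is their own control. Section 6.4 describes the PEMT analysis as confirming that the score agrees with existing knowledge.

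**The concern.** The score is meant to stand in for pool size in individuals whose genotype will usually be unknown. That needs more than a correlation: people with the same pool size should get about the same score whatever their genotype. The plan asserts something close to this but never estimates it, because score and pool size are never placed in one model together with genotype.

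The own-control argument does not help. It protects comparisons between diets within a person, but genotype is fixed within a person, so a genotype contrast is a between-person comparison.

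Two things are at stake. In SubAim 1c, a worse mean score in carriers could be taken as support for the score when part of it is a direct genotype effect on a marker. In later use, a universal formula could flag carriers too often or too rarely at a given pool size.

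**Working it through.** **1. The plan's only genotype power figure.** Section 6.4 gives 89.61% power for a diet-by-genotype effect of 0.6 at P<0.05, without stating n, carrier share, sidedness or within-subject correlation. I treated it as a two-group contrast, with power = Φ(0.6·√(n₁n₂/N) − 1.96).
- 100 women split 44/56 (shares from Section 5.1): 0.6 × √(44×56/100) = 2.98, so Φ(1.02) = 84.6% (83.9% by t).
- 120 enrolled women, same split: 90.4% (89.9% by t).
- 150 subjects at 26/74 (74% from Section 1.1): 89.7% (89.3% by t).
- One group of 50 at 44%: 55.8% (54.1% by t).

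The figure is attainable, but the inputs behind it cannot be identified. It also concerns the interaction, which step 2 shows is a different quantity.

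**2. What the planned models can see.** Write score = a + b·pool + δ·carrier, where δ is a direct genotype offset at equal pool size.
- Genotype difference in mean score on a given diet = b × (genotype difference in pool) + δ. The score model in Section 6.3 estimates this sum and cannot split it.
- Genotype difference in the diet contrast (25% minus 100%) = b × (genotype difference in pool change). A constant δ cancels, so it does not distort the powered interaction.
- The parallel pool-size model estimates the genotype difference in pool. No planned step combines it with the score model to isolate δ, and no rule covers discordant results.

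**3. Does the propionylcarnitine difference matter in scale?** ln(1.5) = 0.405. The depletion-to-baseline ratios for this marker in Appendix Figure 3 are 1.78 (no dysfunction), 1.38 (muscle dysfunction) and 1.02 (fatty liver).
- 0.405 / ln(1.78) = 0.70
- 0.405 / ln(1.38) = 1.26
- 0.405 / ln(1.02) = about 20

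The reported difference is of the same order as the marker's own response to a 10% diet, and the Synopsis expects smaller responses here. That justifies a check. It does not give δ.

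**4. Can correlation survive an offset?** Illustration with assumed inputs: equal pools in both genotypes, carrier share p = 0.44, correlation r = 0.9 without an offset, offset d in score SD. The correlation becomes r/√(1 + d²p(1−p)).

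| d | Correlation | Carriers in worst 20% | Non-carriers in worst 20% |
|---|---|---|---|
| 0 | 0.90 | 20% | 20% |
| 0.25 | 0.89 | 24% | 17% |
| 0.5 | 0.87 | 28% | 14% |
| 1.0 | 0.81 | 35% | 8% |

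For d = 0.5: 0.9/√(1 + 0.25×0.2464) = 0.87. The Synopsis sentence can be true as worded while the score is miscalibrated by genotype.

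**5. What a direct test could detect.** Offset detectable with 80% power, two-sided 0.05, in residual SD of the subject-level score given pool size = (1.96 + 0.84)/√(N·p(1−p)).
- N=150, p=0.44: 2.80/√36.96 = 0.46
- N=150, p=0.26: 2.80/√28.86 = 0.52
- N=100, p=0.44: 2.80/√24.64 = 0.56
- N=50, p=0.44: 2.80/√12.32 = 0.80

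Applying these shares outside premenopausal women is an assumption.

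**The case against.** A reader might infer that the plan's own data show carriers scoring worse at the same pool size. They do not. Section 5.1 says isotope dilution had not been used before for choline pools, so the earlier difference was not compared at equal pool size as this study will measure it. Carriers may simply have had smaller pools, which is the plan's hypothesis, and the marker would then be working correctly. The direction is also unclear: the rise in Figure 3 is largest in people without dysfunction and almost absent in those with fatty liver. Propionylcarnitine's weight is unknown until OPLS-R is run, and one shifted marker among many may matter little. All of this stands.

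A reader might also set the offset against the planned effect of 0.6, or infer a false confirmation of the powered test. Step 2 rules this out for a constant offset.

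It is also fair that Section 6.3 models pool size in parallel and plans post hoc comparisons of metabolites by genotype, so a discordant result could be noticed. What remains missing is a formal test conditional on pool size. Nor will OPLS-R reliably remove a genotype-tagged marker: if carriers do have smaller pools, such a marker predicts pool size in the pooled fit and can earn weight.

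Finally, the added model has its own weakness. Pool size is estimated with error, and Section 5.1 notes that PEMT synthesis dilutes the label. If carriers truly have smaller pools, noisy adjustment leaves about slope × (1 − reliability) × pool difference as an apparent offset. A simulation with no direct genotype effect gave no false offset with error-free pool size, and about 0.05 to 0.16 score SD at an assumed reliability of about 0.8.

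**Conclusion.** The point holds as an untested assumption, not as a demonstrated bias. The plan relies on one score-to-pool relation for all genotypes, uses genotype to validate the score, and has no model that relates score to pool size by genotype. The propionylcarnitine report is a reason to test; it is not evidence of an offset.

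The exposure is the genotype main effect on the score (Section 6.2). Its size cannot be derived: converting a 50% difference into score units needs the marker's between-person SD, the number of markers and their weights, none of which is given. The figures in step 4 show only that correlation is an insensitive check. The change is worth making because it is cheap and replaces two unlinked models with one that addresses the question.

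**What to change.** Add to SubAim 1c one mixed model of the out-of-sample score (predicted with all of that participant's records left out of the fit) on pool size, PEMT genotype and pool size × genotype, with sex/menopause group as a fixed effect and participant as a random effect. Report the genotype offset with its confidence interval, and calibration by genotype, next to the existing pool-size model. Describe a genotype difference in score as worse status only where the pool-size result supports it. Restate the Synopsis sentence as an assumption to be tested. Refit without propionylcarnitine as a sensitivity analysis only; a residual offset alone should not remove a marker or trigger genotype-specific scoring.

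The cost is analysis-plan wording and one extra model, with no new visits or samples. It depends on genotypes being available, and Section 10 defers genotyping until a follow-on study is certain, so the model should be prespecified now and run when they are. State two limits with the result: error in the pool estimate, including PEMT label dilution, can leave a residual genotype term; and at the precision in step 5 a non-significant term does not establish invariance.

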1 BACKGROUND AND RATIONALE

1.1 Introduction

Scientific Premise

Choline (Cho) is an essential nutrient and most Americans' diets do not achieve the recommended intake (2). Diets low in Cho are associated with liver and muscle disease (3-5) and with suboptimal fetal development (6, 7), while diets too high in choline may be associated with increased risk for heart disease (8, 9). There is no validated biomarker for choline status (the availability of the various forms of Cho needed to sustain optimal cellular function); measurement of plasma Cho concentrations is not adequate because plasma choline is homeostatically regulated. Based on extensive preliminary and published data from our lab (10), we identified a panel of potential biomarkers that could be used to assess Cho status, and we propose studies to validate this biomarker panel against measures of Cho pool size using isotope dilution.

Impact

A biomarker panel for assessing Cho status would be used by clinicians and scientists to identify people with depleted choline stores and who may be at risk of developing organ dysfunction due to choline deficiency if their choline intake is not increased. This would enhance clinical care for pregnant women, people with obesity and metabolic syndrome, fatty liver, muscle disease and for people on parenteral nutrition (where choline deficiency is a problem) (11). It would also enhance clinical and epidemiological studies attempting to link choline status to disease risk. Finally, it may permit refinement of recommendations for dietary choline intake.

Innovation

There is no previous work attempting to establish a biomarker panel to assess Cho status. We propose to use cutting edge techniques to develop such a panel. The innovative biomarker panel that we propose for choline status is based on previous work by our research group (10) and has never been considered as markers for choline status prior to the proposed studies. The use of isotope dilution to measure Cho pool size is innovative; though it has been tried for Vitamin A status assessment (12), it has not been attempted for choline status. The investigators have been among the leaders in the area of choline nutrient requirements.

Background:

People need to have a source of Cho: Cho has several important functions. It is (i) a source of methyl-groups needed to make the primary methyl donor, S-adenosylmethionine; (ii) a part of the neurotransmitter acetylCho; and (iii) a component of the major phospholipids in membranes (phosphatidylCho (PtdCho) and sphingomyelin)

(13). The Cho derivative, PtdCho is a main constituent of very low density lipoproteins (VLDL) and is required for VLDL secretion and the export of fat from liver (14). Cho also is important for normal fetal development (15, 16).

Cho is a required nutrient and in 1998, an Adequate Intake (AI) and a Tolerable Upper Limit (UL) for Cho was established (17). In 2016, the US Food and Drug Administration (FDA) set a Recommended Daily Intake (RDI) for Cho based on the AIs as part of the new Nutrition Facts label for packaged foods (published in the Federal Register on May 27, 2016; FDA-2012-N-1210-0875, Federal Register Number:2016-11867). The AI/RDI varies by age and gender, but is 550 mg/d in adult men and 425 mg/d in adult women (more in pregnant and lactating women).

Dietary Cho intake varies over a 3-fold range: There is a wide variation in Cho intake in the diet; in several human cohorts, Cho intake varies by approximately 3-fold – the US National Health and Nutrition Examination Survey (NHANES 2009-2012) data show that only 11% of adult Americans achieve the Adequate Intake level of Cho, with mean intake being 300 mg/day (10%ile being 200 mg/d; 90%ile being 500 mg/d) (2). Similar ranges of intake were reported in the Framingham Offspring Study (18), the Atherosclerosis Risk In Communities study (19, 20) and the Nurse's Health Study (21). Intake of Cho is even lower in low-income countries such as Jamaica and The Gambia (22, 23).

[figure not shown]
Clinical studies show that people fed diets low in Cho develop liver and muscle damage: Diets low in Cho result in fatty liver, liver damage and muscle damage in people (3-5). The dietary requirement is highest for men and postmenopausal women while premenopausal women may have a reduced requirement for Cho, as discussed later (4, 11, 17, 24-26). Nonalcoholic fatty liver (NAFLD), that occurs as humans become obese, can be predicted by a genetic signature (pattern of SNPs) in Cho-related genes (27), and higher dietary intake of Cho reduces the risk of developing fatty liver (28). At present, Cho is not routinely added to commercial parenteral solutions for infants and adults (29, 30). However, adults and infants receiving total parenteral nutrition (TPN) over the long term have low plasma Cho concentrations and often develop hepatic abnormalities, including NAFLD (31-33). In men, dietary intakes in excess of the Cho RDI-AI are needed to optimize homocysteine disposal after a methionine load as well as for the removal of fat from liver (34). A Cho intake exceeding current dietary recommendations was also shown to preserve markers of cellular methylation and attenuate DNA damage in a genetic subgroup of folate-compromised men (35).

Population studies also suggest that there is a range for healthful Cho intake: Women eating diets low in Cho during pregnancy (about 200 mg/d) are more likely to give birth to a child with birth defects than are women eating 500 mg/d (6, 36, 37). However, other studies have found no relationship between plasma or serum Cho concentrations during pregnancy and neural tube defects in offspring (38, 39) (likely because plasma Cho is not an adequate marker of Cho status). In addition, low dietary intake of Cho (about 150mg/d) was associated with decreased cognitive function in the Framingham Offspring Cohort (40). Higher Cho intake in pregnant women in Massachusetts was associated with modestly (but significantly) better child visual memory at age 7 years (41). In one observational study in 2,195 adults aged 70–74 years in Norway, participants with plasma Cho concentrations lower than 8.4 mcmol/L (20th percentile of concentrations in the study population) had poorer sensorimotor speed, perceptual speed, executive function, and global cognition than those with Cho concentrations higher than 8.4 mcmol/L (42). Lower dietary intake of Cho was associated with an increased risk of breast cancer (43, 44) and colorectal cancer (45). Diets low in Cho increased the overall relative risk for developing cancer in a quantitative meta-analysis of 11 papers published on this topic (46), with the largest reported effects found for lung (30% increase; (47)), nasopharyngeal (58% increase; (47)) and breast cancer

[figure not shown]
[figure not shown]
(60% increase; (48)). An increment of 100 mg/day of Cho and betaine (a metabolite derived from Cho) intake helped reduce cancer incidence by 11% (46).

[figure not shown]
At the same time, diets high in Cho may be associated with an increased risk for prostate cancer progression (49), for colorectal adenomas (21) and for heart disease (8, 9). Analysis of data on 80,978 women from the Nurses' Health Study and 39,434 men from the Health Professionals Follow-Up Study found an increased risk of mortality in those consuming higher levels of Cho (50). Thus, it appears that diets at the lower end of normal intake for Cho have adverse health consequences, while diets at the higher end of normal intake also have adverse consequences. This U-shaped risk-benefit curve defines a relatively narrow range for optimal Cho intake, making the development of better biomarkers of Cho status very important.

Genetic variation influences risk for becoming Cho depleted: Single nucleotide polymorphisms (SNPs) in several genes related to Cho and folate metabolism alter the risk for developing organ dysfunction when people become Cho depleted (25, 35, 51, 52). PEMT (phosphatidylethanolamine-N-methyltransferase) catalyzes the formation of Cho moiety as part of PtdCho (53) and this pathway can reduce the amount of Cho that must be obtained from the diet (3). This gene is induced by estrogen; with maximum induction at the concentrations achieved in women during pregnancy (54). Women with the C allele of *PEMT* rs12325817 (74% of Caucasian women) are more susceptible to liver damage when consuming a low Cho diet (51, 55) because this allele abrogates estrogen-induced expression of the gene (56). Other *PEMT* SNPs also increase Cho requirement (rs4646343-A and rs3760188-A) (52). A number of other common SNPs in genes related to choline metabolism alter the requirement for Cho (25, 35, 51, 52, 57-59). Thus, similar dietary intakes may lead to very different Cho status, depending on genotype.

Given the narrow range for healthy intake of Cho, given the establishment of a RDI/AI for Cho to maintain health, given the 3-fold variation in dietary intake in the US, given the effects of common SNPs on the dietary requirement for Cho, and because plasma Cho concentrations do not adequately reflect status (see below), it is important that a good biomarker panel for assessing Cho status be established.

Potential biomarkers for Cho status: Self-reported dietary intake is very hard to measure accurately, and

for Cho we have demonstrated that self-report can significantly underestimate actual intake (60). Thus, we need a set of biomarkers with which to assess Cho status in people. The largest stores of Cho are located in the liver, and mass resonance spectroscopy of liver has been used in the past to assess Cho status in humans (3, 25, 51). This method is not practical for use as a biomarker in clinical or public health practice as it is expensive and the availability of the instrumentation is limited. Liver biopsy is risky and not practical, making measurement of hepatic Cho and Cho metabolite concentrations a poor choice for assessing Cho status. Measurement of Cho concentrations in plasma alone is not an adequate marker for Cho status because Cho concentrations drop quickly to 70% of normal when a person is fed a low Cho diet, but do not decrease further with more severe depletion (3, 4) even in people starved for 7 days (61). The concentrations of PtdCho and sphingomyelin also decrease in people fed a low Cho diet (3, 4), but these phospholipids alone are not adequate biomarkers for Cho status because they are carried as part of plasma lipoproteins, and vary in concentration with changes in fat and cholesterol transport by these particles. Thus, such measurements are useful but not sufficient as biomarkers for Cho status.

Perhaps there is a panel of biomarkers that together will more accurately and reliably reflect Cho status. We admitted people (n=169; 60 premenopausal women, 52 postmenopausal women and 57 men) to our CTSA and fed them a diet containing 100% of recommended intake (550 mg/d) for one week, and then fed them a low Cho diet (10% normal Cho) for up to 7 weeks, or until they developed liver or muscle damage, and then fed them a Cho replete diet until such damage was completely resolved (24, 25, 52, 55). In these carefully controlled studies, using n=44 of the subjects, a comparison of metabolomic profiles between the two diet periods identified a number of potentially useful biomarkers of Cho status (10) (**Figs 2 & 3**).

The concentrations of plasma Cho, betaine, sarcosine, dimethylglycine, methionine, and PtdCho were significantly decreased, and homocysteine was significantly increased during Cho depletion in people (10). Cho

depletion was associated with abnormal renal function in animal models (62); a number of metabolites that accumulate in people with diminished renal function, including 3-carboxy-4-methyl-5-propyl-2-furanpropanoate (CMPF), hippurate and 3-indolepropionate also were significantly increased by Cho depletion in our study subjects (10). Cho is important for mitochondrial function (63, 64), and in our study, plasma concentrations of several acylcarnitines were increased, reflecting perturbed mitochondrial function (65). In addition, people with SNPs that increase susceptibility to Cho deficiency had > 50% increased concentrations of propionylcarnitine (10). Plasma concentrations of a number of amino acids and their metabolites increased in Cho depletion (glutamine, pyroglutamate, glycine, valine, glutamyl-valine, and leucine) (10). Finally, plasma concentrations of a number of metabolites released from dying cells (urate and pseudouridine) were elevated in Cho depleted subjects (10). The alterations associated with Cho depletion in most metabolites were at least partially corrected by Cho repletion (10).

When people were depleted of Cho they developed abnormal aspartate transaminase (AST; marker of liver damage) and creatine phosphokinase (CK; marker of muscle damage) activities in blood (24, 52). This occurs because Cho deficiency induces apoptosis in tissues (26, 66, 67). Development of fatty liver was also a marker for Cho depletion in people fed low Cho diets (24, 25, 52, 55). Previously, we used mass resonance imaging to quantitate the fatty liver that occurred with Cho depletion (24) but this method is expensive and we believe that other non-invasive methods can be used to assess fatty liver. Controlled Attenuation Parameter (CAP) is a new ultrasound-based technique to measure steatosis simultaneously with assessment of liver stiffness using transient elastography (TE); it has been used in research studies (68-72) and is being used in hepatology clinics (73, 74). The measures of organ dysfunction discussed above, could improve a panel of other biomarkers by providing information assessing likely organ effects associated with Cho depletion. Though we expect elevations in these markers, we do not anticipate clinically significant damage based on this study design (see Safety).

Each of the above biomarker measures alone could be changed by multiple physiological inputs, however, based our data from the above study (10), we hypothesize that the combined panel of biomarkers provides a pattern of changes unique to Cho status, with more severe Cho deficiency having larger changes in the biomarkers. We suggest that a score based on some or all of the panel of biomarkers described above will provide a much more accurate and specific assessment of Cho status than measurement of plasma concentrations of Cho or PtdCho alone (**Fig. 4**).

Our preliminary data only represent fully replete and very depleted people, with no information about the people with in-between Cho status. In this grant proposal, we propose to generate data on people with more moderate depletion of Cho and develop a panel of biomarkers and use these measures to develop a Cho status score. By making measurements in people fed incrementally reduced amounts of Cho, and comparing the biomarker measures to body total Cho pool size assessed using isotope dilution (a proxy for the availability of the various forms of Cho), we will be able to identify the combination of biomarkers and algorithm for calculating a Cho status score that best predicts total Cho pool size, and therefore predicts choline nutritional status (the availability of the various forms of Cho needed to sustain cellular function).

